NIH Toolbox Cognition and Motor batteries -@done if participant able to be seen in person		х						Х						х			х
Cognition battery including Attention/exec function (flanker and dimsional change card sort), Episodic memory (Picture seq memory), working memory (List sorting), Processing speed (pattern comparison). Baseline only: Language (Oral reading recognition) Motor battery including Dexterity (pegboard), Strength (using grip dynamometer), Balance,																	
gait speed																	
Psychological well-being (NIH Toolbox self-report measure)		х						х						х	X	х	х
Physical Function (PROMIS)		х						х						х	Х	х	х
Social Participation (PROMIS)		х						х						х	Х	х	x
AE and SAE collection (collected anytime the event occurs)																	
Anxiety (PROMIS)		х															
Done by central rater pool at WU by phone:																	
MADRS		х						х						х	х	х	х
*Typically Week 10; or upon dropout																	
**Central rater pool will assess side effects, falls, and adherence during continuation; local s	ites can do	additional	decisi	on sup	ort cal	lls "as n	eeded	during"	this tim	ne							

F3 Baseline

- Participant signs (or returns signed) informed consent form; all elements of informed consent have been discussed and participants' questions answered.
- Local Research Team Assessments: (in person if possible; approximately 3 hours)
 - MINI MDD & Bipolar Modules
 - PHQ-9 (If more than 7 days has elapsed since the PHQ-9 was done at pre-screen.)
 - Suicide History, Risk & Protective Factors
 - Baseline Side Effects
 - Expectations for Adherence
 - Behavioral Therapy Assessment
 - Falls & Related Injuries (history)
 - Height and Weight (self-reported)
 - If indicated by pre-screen: DAST-10
 - o If indicated by pre-screen: AUDIT
 - NIH Toolbox Psychological Well Being
 - o PROMIS Physical Function
 - o PROMIS Social Participation
 - PROMIS Anxiety
 - NIH Cognition and Motor Batteries (in person assessments may be foregone for participants living in remote locations)
 - o ATHF
 - o CIRS-G
 - Medical Conditions and Medication List (study doctor to review before randomization)
 - Confirm inclusion/ exclusion criteria are met
 - Randomize participant; provide initial decision support per randomization status to participant's doctor.
- Central Rater Assessments (by phone; approximately 30 minutes)
 - o MADRS

F4 Decision Support Calls

- Every 2 Weeks During Acute Treatment: Step 1 Weeks 2, 4, 6, 8, 10* & Step 2 Weeks 2, 4, 6, 8, 10*

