- Phone Call with Local Research Team (approximately 10 minutes)
 - o PHQ-9
 - Spontaneous side effect report & severity
 - Falls Assessment
 - Adherence
 - o Counselling about adherence and management of side effects.
 - AE reports done as needed.
 - Decision support staff contact study MDs when needed (e.g. if confusion about whether to increase antidepressant dose).
 - Decision support staff contact participant's clinical provider with recommendations;
 also will typically tell patient the recommendations.

F5 Acute Phase End Assessments

- Step 1 Week 10, Step 2 Week 10, or upon early withdrawal (if possible)
 - If there is a long delay between the Step 1 Week 10 assessment and the initiation of Step 2, the participant may be asked to repeat some or all of the Step 1 End assessments.
- *In addition to Decision Support assessments, local research team will conduct the following assessments (in person if possible; approximately 1 ½ hour):
 - NIH Toolbox Psychological Well Being (may be conducted via phone or Redcap survey)
 - PROMIS Physical Function (may be conducted via phone or Redcap survey)
 - o PROMIS Social Participation (may be conducted via phone or Redcap survey)
 - NIH Cognition and Motor Batteries (may be foregone for participants living in remote locations)
 - Weight (self-reported)
- Central Rater Assessments (by phone; approximately 30 minutes. WU participants may do in person or by phone)
 - o MADRS

F6 Continuation Assessments

- Months 4, 8, and 12 after completing acute treatment in Step 1 and/or 2 as indicated.
- Participants who relapse in Continuation after Step 1 may be invited to participate in Step 2; and then continuation subsequently.
- Local Research Team Assessments (in person if possible; approximately 1½ hour)::
 - NIH Toolbox Psychological Well Being (may be conducted via phone or Redcap survey)
 - PROMIS Physical Function (may be conducted via phone or Redcap survey)
 - o PROMIS Social Participation
 - Weight
 - NIH Cognition and Motor Batteries (Month 12 only; may be foregone for participants living in remote locations)
- Central Rater Assessments (by phone; approximately 30 minutes)
 - o MADRS
 - Falls & Related Injuries
 - Spontaneous side effects and severity(discuss with local sites if needed)
 - Adherence

F7 Genetic Testing

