A priori, specific plans for data analysis correspond to major aims and will be directed by Co-I [name], professor of biostatistics at the coordinating site.

We will follow the intention-to-treat (ITT) principle. In other words, patients who receive coprescribed medications stop randomized medication, or switch to a different medication will continue to be followed. To confirm that ITT findings represent the "true" data on effectiveness, safety, and tolerability of management strategies, we will conduct a sensitivity analysis that will compare ITT to per-protocol findings.

H1a (Psychological Well-Being): We will use a repeated measures 2*2*3 ANOVA with age (60-70, >70), time (baseline, end of Active phase of Step 1) by treatment group (3 levels). Specific time* treatment group contrasts will compare the changes across pairs of treatment groups. These tests will be conducted with a significance level of .05/3. We will include site as a strata in all analyses. For those who proceed to Step 2, analogous repeated measures 2*2*2 ANOVA will be used with a significance level of .05 for the time*treatment group comparison.

H1b (remission): Corresponding 2*3 (age by treatment group) generalized linear models with a logit link function will be computed for the dichotomous outcome of remission.

In the **continuation phase** we will explore the long-term effectiveness of antidepressants: We will test for preservation of psychological well-being and other quality of life variables, and sustained resolution of depressive symptoms, by mixed effects repeated measures models.

We will also test for sustained remission by measuring relapse in each arm. Relapse will be defined as meeting DSM 5 criteria for a major depressive episode, as determined by an Independent Evaluator who will confirm the diagnosis by conferring with a study investigator. We will carry out Cox models examining time to relapse and time to dropout, to examine for treatment inferiority (i.e., whether one antidepressant strategy produces poorer long-term outcomes). Based on our prior research we don't have an empirical basis to posit a specific arm as inferior. Therefore, although these analyses are important to our stakeholders, we describe them as exploratory.

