3.7. Timing of outcome assessment

Outcome assessment will be conducted at the end of the acute phase for both step 1 and step 2. During the continuation phase, assessments will be conducted at month 4, month 8, and month 12.

4. Statistical principles

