6.1. Outcome definitions

6.1.1. Primary and secondary outcomes

Primary: Psychological well-being is the patient-centered effectiveness outcome (H1a) and remission from depression is the clinician-focused effectiveness outcome (H1b). Safety will be monitored through serious adverse events (H2a) as well as falls and fall-related injuries (H2b).

Secondary: Secondary tests of effectiveness will examine changes in other aspects of quality of life: physical function, social participation, changes in depressive symptoms (i.e., MADRS scores), and antidepressant response (i.e., 50% or more reduction from baseline MADRS).

Continuation phase analyses (all are considered secondary):

In the continuation phase, we will explore the long-term effectiveness and safety of antidepressants:

- We will examine long-term changes/stability of psychological well-being and other quality of life variables, and depressive symptoms, by mixed-effects repeated measures models.
- We will also test for sustained remission (among those who achieved remission at the end of the acute step) by measuring relapse in each arm. Relapse will be defined as meeting DSM 5 criteria for a major depressive episode, as determined by an Independent Evaluator − who will identify all remitted participants who then have a criterion-based (ie PHQ9 score of 2-3 for items 1-8, 1-3 for item 9) and who will confirm the diagnosis by conferring with a study investigator. We will carry out Cox models examining time to relapse (primary: meeting PHQ-9 criteria for a current MDE; secondary: MADRS ≥ 15).and time to drop out, to examine for treatment inferiority (i.e., whether one antidepressant strategy produces poorer long-term outcomes).
- In the continuation phase, we will also explore the long-term safety of antidepressants. **Serious adverse events** are the safety outcome in both acute and continuation phases. Cox models examining time-to-event (with Anderson & Gill extensions for repeated events) will compare the treatment arms during continuation in terms of serious adverse events. Since falls and fall-related injuries information were not collected during the acute phase, the safety endpoint has changed. A time-to-event analysis will not be appropriated. Hence, a generalized linear model with logistic link function will be used.

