6.6. Statistical software

Data cleaning and statistical analyses will be performed using SAS (SAS Institute, Cary NC) and R (The R Foundation for Statistical Computing; Vienna, Austria).

⁸ Describe how you will examine sensitivity of inferences to missing data methods and assumptions, and incorporate into interpretation.

⁹ Describe statistical methods to handle missing data.

¹⁰ Describe plans to use validated methods to deal with missing data that properly account for statistical uncertainty due to missingness.

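### The SAP fixes neither a relapse-dating rule nor a tie method for the Cox model of relapse, which is sought at three scheduled visits; one permitted combination of choices weakens the comparison

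*SAP*

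**What the plan says.** SAP 6.1.1 gives the model and two relapse definitions: "We will carry out Cox models examining time to relapse (primary: meeting PHQ-9 criteria for a current MDE", with a MADRS score of 15 or more as the secondary definition. Its purpose is to see whether any strategy does worse in the long term. The same section classes all continuation analyses as secondary; protocol section H1 calls these analyses exploratory.

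On timing, SAP 3.7 states: "During the continuation phase, assessments will be conducted at month 4, month 8, and month 12". Protocol F6 agrees: "Months 4, 8, and 12 after completing acute treatment in Step 1 and/or 2 as indicated".

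On who decides, protocol H1 defines relapse as a DSM-5 major depressive episode, "as determined by an Independent Evaluator who will confirm the diagnosis by conferring with a study investigator". Neither document says which date a relapse then carries.

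On software, SAP 6.6 states: "Data cleaning and statistical analyses will be performed using SAS (SAS Institute, Cary NC) and R". No option for ties is named.

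Two provisions allow relapse to come to light between visits. The footnote to the schedule in protocol F2 says "Central rater pool will assess side effects, falls, and adherence during continuation" and lets local sites add decision support calls as needed; under F4 such calls include the PHQ-9. F6 adds: "Participants who relapse in Continuation after Step 1 may be invited to participate in Step 2; and then continuation subsequently".

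**The concern.** The Cox partial likelihood is built for event times that are continuous or nearly so. If relapse is recorded at the nominal visit month, all relapses found at one visit share one event time, and a year of follow-up has three distinct times. With ties that heavy, the estimate depends on the tie method. Breslow's approximation pulls the hazard ratio toward 1; Efron's largely does not.

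The plan as written therefore does not determine a single result. The same data could give two hazard ratios and two p-values, depending on a software option and a coding habit. One of those results makes a worse long-term strategy harder to detect, among a fairly small number of remitters.

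**Working it through.** The documents give no event count, hazard ratio or power for relapse, so there is no planned figure to reproduce.

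**Inputs from the documents**
- Step 1 participants at the revised size (SAP 3.3): 708 − 123 = 585, or 585/3 = 195 per arm.
- Remission of 40% (protocol H2, power table): 195 × 0.40 = 78 remitters per arm. With the 45% in the protocol K4 milestones: 195 × 0.45 = 87.75.
- At the planned 1,500 with 45% remission: 1,500 × 0.45/3 = 225 per arm.
- Continuation drop-out of 10% over the year (protocol K4).

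**Assumptions not in the documents**
- 12-month relapse in the reference arm: 30-50% in the main runs, 20-60% in the wider runs.
- True hazard ratio (HR) of 1.0, 1.5 or 2.0, with exponential relapse times.

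**Step 1: how heavy the ties would be.** Take 80 per arm, 40% relapse and HR 1.5.
- Monthly hazards are λ = −ln(0.6)/12 and 1.5λ; drop-out is μ = −ln(0.9)/12.
- Expected relapses found at visit s = 80 × Σ over arms of [exp(−4h(s−1)) − exp(−4hs)] × exp(−4μs), where h is the arm's hazard.
- Result: 29.5, 22.9 and 17.8, so about 70 events on three times.
- Over 20-60% relapse and HR 1.5-2.0, the total is about 36 to 109 events.

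**Step 2: main example.** 78 per arm, 40% relapse, true log HR = ln 1.5 = 0.405, 3,000 trials per setting. The date-spread rows are a separate set of runs with the same settings, in which nominal months with Breslow gave 0.367 and 29% power.

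| Analysis | Mean log HR | Mean model SE | Sampling SD | Power |
|---|---|---|---|---|
| Nominal months, Breslow | 0.363 | 0.247 | 0.225 | 28% |
| Nominal months, Efron | 0.401 | – | – | 37% |
| Grouped model (cloglog) | 0.404 | 0.247 | 0.250 | 37% |
| Dates spread ±7 days, Breslow | 0.405 | 0.248 | 0.245 | 37% |
| Dates spread ±14 days, Breslow | 0.395 | 0.248 | 0.253 | 36% |

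With nominal months and Breslow:
- Attenuation: (0.405 − 0.363)/0.405 = 10%.
- Model SE against its own sampling SD: 0.247/0.225 = 1.10.
- Power loss: 37 − 28 = 9 points.

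**Step 3: range at 30/40/50% relapse, 78 per arm, nominal months.**
- Log HR attenuation under Breslow: 6-15%.
- Power at HR 1.5: 26/28/32% (Breslow) against 31/37/44% (grouped model), a loss of 5, 9 and 12 points.
- Power at HR 2.0: 69/77/83% against 75/84/91%, a loss of 6, 7 and 8 points.
- Type I error under Breslow: 3.1-3.5%. The wider runs gave 2.5-3.5%.

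**Step 4: dependence on the assumed relapse rate.** 225 per arm, nominal months; attenuation = 1 − (mean Breslow log HR)/(true log HR).

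| 12-month relapse | True HR | Breslow log HR | Attenuation | Efron log HR |
|---|---|---|---|---|
| 20% | 1.5 | 0.384 | 1 − 0.384/0.405 = 5% | 0.402 |
| 20% | 2.0 | 0.665 | 1 − 0.665/0.693 = 4% | 0.701 |
| 40% | 1.5 | 0.369 | 1 − 0.369/0.405 = 9% | 0.409 |
| 40% | 2.0 | 0.610 | 1 − 0.610/0.693 = 12% | 0.688 |
| 60% | 1.5 | 0.335 | 1 − 0.335/0.405 = 17% | 0.402 |
| 60% | 2.0 | 0.556 | 1 − 0.556/0.693 = 20% | 0.687 |

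The distortion is small when relapse is rare and grows with the number of relapses per visit. Efron stays close to the truth throughout.

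**The case against.** The strongest reply is that the ties are not in the documents. A visit schedule is not a statement that analysis time is the nominal month, and each participant's clock starts at their own end of acute treatment. If actual assessment dates are used, few relapses coincide exactly. In the date-spread runs, attenuation under Breslow then fell to 0-5% over 30-50% relapse and HR 1.5-2.0, with type I error of 4.3-5.7%. This stands, and it makes the concern conditional.

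Second, a reader might infer that every relapse in a four-month window must share one event time. That is not established for the primary definition, which rests on the PHQ-9. F6 does not list the PHQ-9 at months 4, 8 and 12, whereas the as-needed calls include it. Relapses found on those calls could carry off-schedule dates. This stands too, and it shows a related gap: the plan does not say where the PHQ-9 used for relapse is collected in continuation.

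Third, a reader might infer that Breslow gives a visibly wider interval. It does not: in the main example its mean SE equals that of the grouped model (0.247). The SE is too large only against Breslow's own, narrower sampling spread. The conservative test and the lost power follow from that and the attenuation; they are not additional faults.

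Fourth, since Efron nearly matches the grouped model, replacing Cox is not essential. That is correct. What remains is that neither the dating rule nor the tie method is stated, and the plan should not leave them to a default.

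**Conclusion.** The concern holds as a gap in specification. With nominal months and Breslow ties, which the plan permits, the log HR is attenuated by about 6-15% at an assumed 30-50% relapse, type I error is about 2-4%, and power falls by roughly 5-12 points. These sizes rest on 78 remitters per arm, 10% drop-out, proportional hazards and a relapse range that the documents do not supply. At 20% relapse the effect is slight.

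A reader might go further and conclude that Cox is the wrong model or that the planned hazard ratio will be biased. The documents do not support that: they fix neither the time coding nor the tie method, and either Efron ties or assessment dates spread over one to two weeks remove most of the distortion. Nor does the problem create false findings of inferiority, because the error is conservative. Serious adverse events are recorded when they occur, so the SAE analysis is not affected. As the relapse analysis is secondary in the SAP and exploratory in the protocol, the priority is minor.

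**What to change.** In SAP 6.1.1, for both relapse definitions, choose one of:
- a grouped-time proportional hazards model: binomial, complementary log-log link, one intercept per visit interval (to months 4, 8 and 12), with treatment, site and age stratum. The exponentiated treatment coefficient is still a hazard ratio; or
- the Cox model with Efron ties named explicitly.

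In either case:
- state that relapse is dated by the assessment at which it is found;
- for the grouped model, assign a relapse found between visits to the interval in which it falls, and say how a participant lost within an interval is counted;
- say at which continuation contacts the PHQ-9 used for relapse is collected.

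Cox can stay for time to drop-out and for serious adverse events.

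The cost is a few sentences and a few lines of code, with no new data. The downside of the grouped model is that it discards the exact date of any off-schedule relapse; if many are expected, Cox with Efron ties keeps that information.

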6.1.2. Outcome measurements

H1a outcome will be measured by NIH Toolbox (Psychological Well-being), and the secondary outcome will be measured by PROMIS (Physical function, Social participation).

H1b outcome will be assessed by independent (blind) raters via phone interview to assess the MADRS score.

H2a outcome will be measured when SAE occurs.

H2b outcome will be assessed by independent raters.

6.2. Analysis methods

To test hypothesis H1a (psychological well-being), a repeated measure of 2*2*3 ANOVA with age (60 – 70, > 70), time (baseline, end of Active phase of Step 1) by treatment group (3 levels) will be used. Specific time * treatment group contrasts will compare the changes across pairs of treatment groups. These tests will be conducted with a Hochberg Step-down procedure. If the comparison with the lowest p-value < 0.05/3 it is significant. If the second lowest p-value is also < 0.05/2 then it also will be significant and if the third p-value is < 0.05 then it also will be significant. We will include site as strata in all analyses. For those who proceed to Step 2, analogous repeated measures 2*2*2 ANOVA will be used with a significance level of .05 for the time*treatment group comparison.

To test hypothesis H1b (remission), a corresponding 2*3 (age by treatment group) generalized linear models with a logit link function will be computed for the dichotomous outcome of remission. Pairwise treatment groups will be compared as in H1a.

To test hypothesis H2a (serious adverse events), Cox models will be used to examine time to event (with Anderson & Grill extensions for repeated events) will compare the treatment arms during both the acute phase and the continuation in terms of serious adverse events. Pairwise comparison between treatment groups will be tested.

To test hypothesis H2b (falls and fall-related injuries), a repeated measures generalized linear model with a cumulative logistic link function. The factors will be treatment group and time (week 2, 4, 6, 8 or 10). The age group (<70 vs.>70) and clinic stratification variables will be included in the model as well as the fall history obtained at baseline. Pairwise comparisons between the treatment group pairs will be formally tested. The same model with a simple logistic link function will be conducted during each 2-week period where the response is a fall-related injury or not.

In terms of the exploratory hypothesis 3, we will include the treatment by age group (<70 vs >70) by time interaction to the linear models described above to test for both the benefits and risks for the treatment alternatives. Additionally, we will fit a model with age as a continuous variable.

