2.2.2. Hypothesis

Theme 1: Benefits and risks of antidepressants: outcomes that matter for patients and clinicians

- 1. Effectiveness. Augmentation arms will show greater improvement than monotherapy arms for effectiveness outcomes.
 - a. Wellness outcome: Improved psychological well-being. (H1a)
 - b. Symptom outcome: Remission from depression (defined as MADRS ≤10 at Step end).
 (H1b)
- 2. Safety. Augmentation arms will have more tolerability and safety concerns (i.e., more serious adverse events) than monotherapy arms.
 - a. Serious adverse events (H2a), falls, and fall-related injuries (H2b) are the safety outcomes.

The primary analytic strategy is a test of specific treatment strategies (e.g., aripiprazole augmentation). More recently, a report on these strategies in mixed-age veterans with TRD (Mohamed et al, JAMA 2017) has suggested that augmentation approaches yield higher remission rates than does switch. The TRD field has, likewise, converged on the overarching question of whether augmentation is superior to switch, more so than the specific question of which augmentation approach is superior (e.g., Ruberto, Jha, & Murrough, "Pharmacological treatments for patients with treatment-resistant depression", Pharmaceuticals 2020; Voineskos, Daskalakis & Blumberger, "Management of treatment-resistant depression", Neuropsychiatr Dis Treat 2020) with a recent Cochrane systematic review (Davies et al, 2019) determining that augmentation strategies appeared efficacious while switch strategies had uncertain efficacy.

For this reason, a secondary analysis of each hypothesis will test the overall strategy of augmentation vs. switch. The two augmentation arms in Step 1 will be summed and compared to the switch arm.

Theme 2: Aging influences the balance of benefits and risks of antidepressant strategies.

3. Moderator analyses (Heterogeneity of Treatment Effect). Exploratory analysis (HT-1): Effectiveness and safety differences between treatment arms will be moderated by age. Specifically, with increasing age effectiveness differences between treatment arms will decrease, and safety differences between treatment arms will increase. In addition, the following potential moderators will be assessed: executive function, co-morbid medical burden, co-morbid anxiety, and degree of treatment resistance.

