4.1. Confidence intervals and p values

To test our primary hypothesis (H1a), a significance level of .05/3 will be considered as statistically significant in Step 1. A significance level of .05 will be considered statistically significant in Step 2. If the significance level is greater than .05, we will emphasis the increased chance of a type I error. Results will be presented with their values (e.g. regression coefficients, standard deviation, etc.) with 95% confidence intervals.

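### The Step 1 step-down levels in SAP 6.2 are valid but stricter than three pairwise contrasts among three arms require: after a first rejection at .05/3, the other two can each be tested at .05

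*SAP*

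**What the plan says.** SAP 6.2 compares the three Step 1 arms in pairs within one model: "Specific time * treatment group contrasts will compare the changes across pairs of treatment groups". On multiplicity it names a method: "These tests will be conducted with a Hochberg Step-down procedure". The levels it then lists are .05/3 for the smallest p-value, .05/2 for the next and .05 for the largest, each step depending on the one before. The middle level is the one at issue: "If the second lowest p-value is also < 0.05/2 then it also will be significant". For remission, 6.2 carries the rule over: "Pairwise treatment groups will be compared as in H1a".

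SAP 4.1 gives one level and no step-down: "To test our primary hypothesis (H1a), a significance level of .05/3 will be considered as statistically significant in Step 1". Protocol H1 likewise gives .05/3 for each pairwise test.

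The effectiveness hypothesis in SAP 2.2.2 is worded for the augmentation arms in the plural: "Augmentation arms will show greater improvement than monotherapy arms for effectiveness outcomes". In Step 1 there are two such arms and one switch arm.

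**The concern.** The levels .05/3, .05/2, .05 are Holm's. Holm protects against every combination of true and false nulls. Among three arms one combination cannot occur: exactly two true nulls. If aripiprazole augmentation equals switch and bupropion augmentation equals switch, the two augmentation arms equal each other. The halving at the second step guards against that impossible case.

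What is at stake is power for the second contrast. A reader of SAP 2.2.2 will want to know whether each augmentation arm beats switch, and the second of those comparisons is the one held to .025. The revised sample size in SAP 3.3 leaves little power to spare.

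**Working it through.** **Inputs**
- SD 8 at both times and r = .5 (Protocol H2, table footnote), so SD of change = √(64 + 64 − 2 × .5 × 64) = 8.
- Original size: 500 per arm at level .05/3 (Protocol H2).
- Revised size: 708 − 123 = 585 in Step 1 (SAP 3.3). With 1:1:1 allocation (Protocol E 1.b), 585 / 3 = 195 per arm. An equal split and no missing outcomes are assumed.
- Relevant change: 2 to 3 T-score points (Protocol H2).
- Two-sided tests are assumed, since the documents do not state sidedness.

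**Reproducing the plan's figures.** Detectable difference = 8 × √(2/500) × (z for .05/3 two-sided + z for power).
- Power .8: 0.506 × (2.394 + 0.842) = 1.64 (plan: 1.6).
- Power .9: 0.506 × (2.394 + 1.282) = 1.86 (plan: 1.9).

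Both agree, so the inputs and two-sided testing are sound. The written levels equal Holm's .05/3, .05/2, .05/1.

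**Why .05 is enough at the second step.** Take levels .05/3, then .05 and .05 (Shaffer), and go through the possible states:
- All three nulls true: an error needs the smallest p-value below .05/3. By Bonferroni the probability is at most 3 × .05/3 = .05.
- Exactly two true: impossible.
- Exactly one true: an error needs that one contrast to have p < .05, so the probability is at most .05.
- None true: no error is possible.

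The argument needs the three contrasts to come from one model on one scale. That holds for H1a (mean change) and for H1b (log odds).

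**Simulation** (2,000,000 trials per configuration, normal arm means, SD 8).

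Shaffer's family-wise error is .044 with all arms equal and .050, within simulation error, at most when one arm differs.

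Probability of rejecting both false nulls when one arm (switch) differs from the other two:

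| Per arm | Difference | Flat .05/3 (SAP 4.1) | Written rule (SAP 6.2) | Shaffer |
|---|---|---|---|---|
| 195 | 2.0 | .363 | .425 | .518 |
| 195 | 3.0 | .840 | .878 | .920 |
| 500 | 1.6 | .659 | .718 | .793 |
| 500 | 2.0 | .897 | .925 | .954 |

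Probability of at least one correct rejection at 195 per arm and 2.0 points: .696 under both the written rule and Shaffer, because the first step is the same.

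**One contrast at .025 against .05, 195 per arm**
- Detectable difference at 80% power: 8 × √(2/195) = 0.810; 0.810 × (2.241 + 0.842) = 2.50 points against 0.810 × (1.960 + 0.842) = 2.27 points.
- Remission 40% against 50%: power .398 against .510.

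**What the gain costs.** At 195 per arm with switch 2.0 points below both augmentation arms, the chance of wrongly declaring those two arms different rises from 2.9% (.0285) to 4.7% (.0466).

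**The case against.** The strongest reply is that nothing here is wrong. The written rule is a standard procedure that holds 5%, and choosing a sharper one is a preference about efficiency. That stands: a reader might infer that the plan's test is invalid or inflates error, and it does neither.

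Three further objections also stand in part.

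- **Two wins are not required.** A reader might infer from the plural wording in SAP 2.2.2 that the trial succeeds only if both augmentation arms beat switch. The section sets no such criterion. It makes tests of specific strategies primary and adds a pooled augmentation-against-switch comparison as secondary. Both-contrast power is therefore one relevant measure, and the one on which the change helps most.
- **The change is not free of downside.** Shaffer rejects everything the written step-down rule rejects, but 6.2 names Hochberg, which is a step-up method. With equal standard errors, p-values of .018, .024 and .91 are possible (z = 2.366 and 2.257; their difference, 0.109, gives p = .91). Hochberg rejects two because .024 < .025. Shaffer rejects none because .018 > .0167. Such cases arise in up to about 0.4% of simulated trials. Shaffer still shows both differences more often (.518 against .432 for Hochberg at 195 per arm and 2.0 points).
- **Timing.** A reader might assume the levels can still be changed before results are seen. SAP 3.6 says the plan was posted before any analyses. However, footnote 1, attached to SAP 4.3, reports something noticed while effectiveness analyses were under way. For this version of the SAP, ignorance of the results cannot be assumed.

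The size also depends on inputs. The 195 per arm ignores dropout, although Protocol K4 assumes 8% in each step. At 2.0 points both-contrast power is only about 52% even after the change.

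**Conclusion.** The point holds as one of lost efficiency. For three pairwise contrasts among three arms, the second level in SAP 6.2 is half of what 5% family-wise control allows. Control here is per outcome: SAP 6.1.1 lists both H1a and H1b as primary, and the rule does not adjust across them.

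In the 2 to 3 point range that the protocol calls minimally relevant, the written rule gives up about 9 to 4 percentage points of power to show both augmentation arms better than switch at 195 per arm (.518 − .425 = .093; .920 − .878 = .042). At 500 per arm and 2.0 points the loss is about 3 points (.954 − .925 = .029). If the flat .05/3 of SAP 4.1 governs instead, the loss at 195 per arm and 2.0 points is larger: .518 − .363 = .155. These figures assume an SD of change of 8, two-sided tests, an equal split of 585 and complete outcomes.

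**What to change.** In SAP 6.2, for Step 1 H1a and H1b, keep the first level and replace the second. Suggested text: *If the smallest of the three pairwise p-values is < .05/3, that contrast is significant and the other two contrasts are each tested at .05 (Shaffer); otherwise none is significant.* Drop the name Hochberg, since the procedure is step-down, and bring SAP 4.1 into line so that one rule governs Step 1. Step 2 has a single contrast at .05 and is unaffected.

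The cost is a few sentences of SAP text, a partial-null error rate closer to 5%, and the rare cases in which a true Hochberg step-up would have rejected and Shaffer does not.

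If results by arm are already known, do not loosen the primary rule. Keep the written levels as primary, and report the Shaffer result as a sensitivity analysis with the date on which it was added.
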